2.2 Safety

[figure not shown]
The primary safety outcome of the study will be the rate of Serious Adverse Events (SAEs) during study episodes defined in this study as death or substantial prolongation of hospitalization, as patients are hospitalized as part of having a qualifying hyperammonemia episode. Safety tests consisting of complete blood count (CBC), liver and kidney function tests, coagulation profile (PTT/INR) will be performed before treatment, on the third day of treatment, just prior to episode treatment completion of NCG and thirty days (up to six months) after the last study dose. Patients in a hyperammonemia crisis frequently experience transient anemia once appropriately hydrated during an emergency room visit. In order to monitor the transient anemia, in addition to collecting CBC's, if a patient receives a blood transfusion during hospitalization this information will also be collected. An EKG test will be performed before treatment and between days 3-5 of treatment or before discharge if earlier.

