3 STUDY DESIGN

3.1 Overview of Study Design

This will be a double-blinded, placebo controlled randomized clinical trial to evaluate the efficacy of NCG in the treatment of two organic acidemias (severe PA and MMA), and two urea-cycle disorders (late-onset CPSD and OTCD). Figure 3 summarizes the design of the proposed trial.

Figure 3. Study Overview Diagram

Protocol Overview

- Eligibility** – Briefly, subjects (a) aged >1 week with verified diagnosis of CPSD or OTCD or (b) subjects of any age with verified diagnosis of PA or MMA and ammonia level \geq 70mcmol/L. All subjects (or a first-degree relative) must have had a recorded plasma ammonia \geq 100 mcmol/L and must have presented initially at >1 week of age for CPSD or OTCD. Subjects must not be pregnant. A complete listing of eligibility criteria is included in Section 4 (Study Population).
- Enrollment** – Informed consent from the participant or one parent or legal guardian.
- Randomization** – At each hyperammonemic episode, participants will be randomized to either placebo plus standard therapy (PLBO-STD) or NCG plus standard therapy (NCG-STD) at a dose of 150 mg/kg/ day or 3.3 g/m²/day for patients >15 kg, divided into 2 equal doses and administered enterally by nasogastric or gastrostomy tube or by oral syringe.
- Study Treatment** – The NCG/PLBO dose will be administered for metabolic decompensation for 7 days or until discharge, whichever is shorter.
- Concomitant Standard Treatment** – Participants will continue receiving standard treatment which may include intravenous glucose (and insulin if required), L-carnitine dosing and/or dialysis. Ammonia scavengers may only be administered in patients with urea cycle disorders.

- **Laboratory Measurements** – Plasma ammonia testing should be performed as clinically indicated, including checking the level at admission and at least every 6-12 hours for the first 48 hours and every day thereafter if the previous level was ≥ 50 $\mu\text{mol/L}$, for a total of 7 days or until discharge, whichever is shorter. Plasma amino acids should also be checked as clinically indicated at admission and at least every 2 days thereafter, if ammonia levels are measured. Safety laboratory assessments including complete blood cell count, liver and kidney function tests, amylase and lipase testing, as well as a coagulation profile (if clinically indicated) will be done at the time of initial admission, at 3-5 days, at 6-7 days or at discharge, whichever is shorter.

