5.4.1.4 Discharge Procedures

If still on NCG/PLBO, the subjects will be discontinued from the study drug at the time of discharge from the hospital.

We will contact subjects or their families to collect any adverse events that occurred in the 72 hours following episode treatment completion.

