7.1.2 Collection and Reporting of Adverse Events

The site study coordinator is responsible for collecting and recording all clinical and laboratory data. Adverse events will be collected on subjects on each day of admission, as well as by phone or e-mail communication with parents when the study coordinator contacts subjects or their families to collect any adverse events that occurred in the 72 hours following episode treatment completion following each admission. The reporting period for new AEs is the period from the start of study drug administration until the patient completes their participation in the study (i.e., until the end of the study period or until discontinuation if early withdrawal occurs). Follow-up reports on AEs should continue up to 30 days after the administration of study treatment if the AE did not resolve.

For each AE, the site investigator will assess severity, and whether the event meets the definition of a serious adverse event (see Section 7.1.1) and will report whether study treatment was interrupted or stopped, as well as the outcome of the AE. If the event is an SAE, both the site PI and the Medical Monitor will assess the relationship to study treatment. As described in 5.7.3, treatment assignment should not be unblinded unless the Medical Monitor assesses that knowledge of drug assignment is required in order to assess how to treat a safety concern within a patient.

[figure not shown]
If a non-serious adverse event is unresolved at the time of discharge from the study, the site PI will make a clinical assessment as to whether continued follow-up of the AE is warranted. The

site PI may request input from the Medical Monitor. Resolution is defined as the return to baseline status or stabilization of the condition with the expectation that it will remain chronic.

The CNMC-CC will prepare aggregate reports of all adverse events (serious/not serious and expected, unexpected) for the DSMB as required and for the FDA on an annual basis. Local site investigators are also required to fulfill all reporting requirements to their IRB and to the CNMC-CC.

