8.1.2 Secondary Aim

Secondary analyses will also evaluate the safety of NCG. Safety is a secondary aim because there is already evidence that NCG, which is approved by the FDA for use in the treatment of NAGS, poses no serious risks to patient safety. Therefore, the focus of this research is less on safety than on its effectiveness in treating PA and MMA, which share the common risks associated with hyperammonemia with NAGS. The analysis of safety will focus on three outcomes; these include the level of selected laboratory markers related especially to organ health, the frequency of reported symptoms, and the frequency of reported adverse events by seriousness. The analysis of laboratory markers will compare the time specific and time averaged mean levels of each marker by study group. In addition, we will compare the frequency of symptoms and adverse events, relying mainly on tabulations by a study group of reports by organ system paying most attention to the magnitude of the difference between groups and consistency of the evidence than on formal hypothesis testing.

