Secondary efficacy outcomes are based on groupwise comparisons of the trajectory (slope) of ammonia decline, FSS, and time-to-hospital-discharge during hyperammonemia episodes. For analysis of the ammonia decline trajectory and FSS analysis, we will implement longitudinal linear hierarchical models. The models will enable us to estimate and compare the slope(s) based on ammonia change trajectory over time, as well as the time, averaged FSS across all episodes treated with NCG vs. PLBO. For time to discharge comparisons, we will rely on the same Cox Regression Analysis described for the primary outcome except the outcome event will be limited to time to discharge. As in the primary analysis, we will adjust model error for the clustering of observations by patient and control for severity based on ammonia level or FSS at admission to each episode. To assess NCG safety we will compare the levels/frequency of laboratory test results, reported symptoms, and adverse events. Secondary analyses will control for indicators of episode severity, e.g. peak ammonia.

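### Adverse events are compared as raw frequencies although observed time per episode depends on discharge, so the comparison can understate events on NCG if NCG shortens stay

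*Combined protocol and SAP*

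**What the plan says.** Section 8.1.2 sets out the adverse event comparison: "we will compare the frequency of symptoms and adverse events, relying mainly on tabulations by a study group of reports by organ system". It puts more weight on the size of the group difference and the consistency of the evidence than on formal testing. Section 8.3 repeats the approach: "To assess NCG safety we will compare the levels/frequency of laboratory test results, reported symptoms, and adverse events". The only adjustment it then names is for severity: "Secondary analyses will control for indicators of episode severity, e.g. peak ammonia". Section 2.2 states that "The primary safety outcome of the study will be the rate of Serious Adverse Events (SAEs) during study episodes" and does not say whether the rate is per episode, per patient or per day.

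The length of observation is set elsewhere. Section 3.1: "The NCG/PLBO dose will be administered for metabolic decompensation for 7 days or until discharge, whichever is shorter". Section 5.4.1.4 stops study drug at discharge and has families contacted "to collect any adverse events that occurred in the 72 hours following episode treatment completion". Section 7.1.2: "Adverse events will be collected on subjects on each day of admission", followed by the same 72-hour contact. Section 2.1 includes earlier discharge in the primary efficacy outcome, and Section 8.3 makes time to discharge a secondary outcome.

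Other places imply other windows. Section 7.1.2 runs the reporting period for new events to the end of participation, while the Day 8 entry in Section 5.4.1.3 completes the event log for the last time. Table 1 appears to show a log entry in its Day 30 column, though the table may be damaged in extraction. No section says which window feeds the group comparison.

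**The concern.** Both the in-hospital daily log and the start of the 72-hour follow-up are tied to discharge, and discharge is something NCG is hypothesised to bring forward. If that happens, the arms are observed for different lengths of time per episode. At the same daily event rate, the NCG arm would record fewer events, and a modestly higher daily rate on NCG could tabulate as no difference. Adjusting for severity does not address this. The risk is greatest when the drug works, and it falls on the magnitude of the difference, which Section 8.1.2 treats as the main evidence. The DSMB also weighs safety results at the interim look (Section 8.3.1).

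**Working it through.** **The plan's own figure.** The documents give no figure for event rates or observation time. The nearest is the effect size in Section 8.4: 114 episodes to detect a hazard ratio (HR) of 1.7 with 80% power, two-sided 5%, no censoring. Schoenfeld's formula gives 4 × (1.960 + 0.842)² / (ln 1.7)² = 111.5, or 112 events. Freedman's gives 117. Both are within 3% of 114, so the figure is reproduced closely enough for this purpose. This HR is for the composite of ammonia below 50 µmol/L or discharge, not for discharge alone.

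**Inputs from the documents.** Treatment cap of 7 days or discharge, whichever is shorter (3.1). Follow-up of 72 hours, or 3 days, after treatment completion (5.4.1.4, 7.1.2).

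**Assumptions not in the documents.** Time to discharge is exponential with placebo mean μ of 3 to 6 days. The discharge HR is varied from 1.0 to 1.7. The daily event hazard is constant and the same in both arms.

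**Formula.** Mean treated time per episode is E(μ) = μ(1 − exp(−7/μ)). On NCG, μ is replaced by μ/HR. Mean observed time is E + 3 days.

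| Placebo mean (days) | Discharge HR | Placebo E + 3 | NCG E + 3 | Ratio NCG/placebo |
|---|---|---|---|---|
| 3 | 1.0 | 5.71 | 5.71 | 1.00 |
| 3 | 1.2 | 5.71 | 5.35 | 0.94 |
| 3 | 1.3 | 5.71 | 5.20 | 0.91 |
| 3 | 1.7 | 5.71 | 4.73 | 0.83 |
| 6 | 1.0 | 7.13 | 7.13 | 1.00 |
| 6 | 1.2 | 7.13 | 6.77 | 0.95 |
| 6 | 1.3 | 7.13 | 6.60 | 0.93 |
| 6 | 1.7 | 7.13 | 6.04 | 0.85 |

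For HR 1.3 to 1.7 the ratio runs from 0.83 to 0.93, so observed time is 7 to 17% shorter on NCG. At HR 1.2, with placebo median stay varied more widely from 2 to 7 days, the ratio is 0.94 to 0.96, or 4 to 6% shorter. At HR 1.0 there is no gap.

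**What this could hide.** Equal expected counts need a daily rate ratio equal to the reciprocal of the time ratio: 1/0.93 = 1.08 to 1/0.83 = 1.21. So for HR 1.3 to 1.7, a daily rate 8 to 21% higher on NCG would tabulate as equal.

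**As a proportion of episodes with any event.** With an assumed equal daily hazard of 0.05 to 0.15 and placebo median stay of 2 to 7 days, the NCG/placebo ratio of that proportion is 0.85 to 0.93 at HR 1.7 and 0.92 to 0.97 at HR 1.3, with the 72 hours included.

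**The case against.** Five points weigh on the other side.

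- A reader might infer that observation ends with treatment or discharge. The documents do not support that: Section 7.1.2 continues collection for 72 hours after treatment completion and keeps the reporting period open to the end of participation. Without the 72 hours the time ratio in this model would be 0.64 to 0.87, which would hide a daily rate 15 to 56% higher on NCG. That describes a window the plan does not use.
- A reader might infer that NCG will look safer simply because it is watched for less time. That is conditional. An episode can meet the composite on ammonia alone while the patient stays in hospital on study drug. Section 8.3 also makes discharge depend on the absence of other complications, which NCG is not expected to affect.
- The constant hazard is a strong assumption. If events cluster early in the episode, the lost days carry few events and the gap matters less. An in-episode SAE can itself be a prolonged hospitalisation (2.2, 7.1.1.2), so some harm would lengthen its own observation.
- The episode is the unit of randomisation and analysis (8.4), so events per episode is a legitimate intention-to-treat quantity. Fewer events because the illness was shorter is partly a real benefit. Length of stay is reported too.
- The remedies have limits. A 72-hour window leaves out events found by the day 6 to 7 laboratory tests and many found by the day 3 to 5 tests. It does not equalise ascertainment either: with a placebo mean of 3 days and HR 1.7, 1 − exp(−1.7) = 82% of NCG episodes and 1 − exp(−1) = 63% of placebo episodes are discharged by 72 hours and move from daily logs to family contact. A per-day rate divides by a duration that treatment may change.

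All five stand as limits on the size of the point and on what the fix can do. None supplies a window or a denominator, and the raw count alone cannot separate a shorter illness from shorter watching.

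**Conclusion.** The point holds in a conditional form. The plan compares events as raw frequencies, and the SAE rate has no stated denominator, while observed time per episode depends on discharge. If NCG shortens stay, the comparison can understate its events. Observed time would be about 7 to 17% shorter on NCG at a discharge HR of 1.3 to 1.7, about 4 to 6% at 1.2 and unchanged at 1.0. These sizes rest on exponential stay and an assumed discharge HR, and reading them as missed events needs a constant daily hazard. None of these is in the documents. They do not show that the bias will occur, and they do not support a stronger claim that the safety comparison is invalid. This is a cheap improvement.

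**What to change.** In Sections 8.1.2 and 8.3:

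- Keep the per-episode tabulation by arm as the main table, over one stated window: first dose to 72 hours after last dose.
- Report observation time per episode by arm beside it.
- Add AE and SAE rates per day at risk by arm over the same window, with standard errors clustered by patient. State in Section 2.2 which denominator the SAE rate uses.
- As a supporting analysis, give the proportion of episodes with an event within 72 hours of first dose. Every episode is covered for that period, because collection runs to 72 hours after treatment completion.

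The cost is SAP wording, slightly more analysis and a derived observation time from dates and dose times already recorded (treatment logs, Section 5.6). Because per-day rates use a post-randomisation duration and the 72-hour window omits later events, both should be read beside the per-episode table and should not replace it.

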8.2 Factors for Stratification

Because clinical management practices and referral patterns may vary from site to site, stratification during randomization by the site will ensure that episodes will be balanced across study groups within each site.

8.3 Statistical Considerations

Experience with models evaluating the overall change in ammonia level during episodes following randomization (not divided by treatment group) has demonstrated that the shape of the ammonia curve is more variable and more complex than envisioned during study design. This circumstance has made it difficult to see how to generate a stable model to properly reflect and compare the slope of ammonia decline by treatment group as the primary outcome.

Challenges included the following:

1. The need to introduce curvilinearity in order to model change appropriately; and
2. The need to also rely on piecewise regression models to adequately model bends or points of inflection in the curve.

The latter has proven especially difficult to manage because methods vary in their recommendation regarding the number (1 vs 2) and position (time point of each bend) to define piecewise regression segments. This variability would lead to the need to create a number of alternative models that would affect the interpretation of results with no clear way to prioritize the choice of the final model.

This situation prompted us to choose an alternative composite outcome and modeling strategy based on time to reach an ammonia level of 50 $\mu\text{mol/L}$ or time to discharge whichever occurs first. This approach avoids the complexity of modeling the correct shape of the ammonia decline curve but provides a rigorous, well-defined, and clinically-relevant outcome for comparison of treatment effects.

Short-Term Outcome of NCG in Hyperammonemia

The choice of 50 $\mu\text{mol/L}$ as the target for ammonia decline is based on the extensive experience of metabolic physicians that a patient reaching this level of ammonia is no longer at risk of acute hyperammonemic injury and would be a candidate for discharge in the absence of other complications, which are not hypothesized to be affected by treatment with NCG.

We propose to use Cox Proportional Hazard modeling to implement the primary analysis to compare the average differences in time to reach the composite outcome and allow us to control for differences in severity (ammonia level and or FSS) at episode baseline. This method will also allow us to take account of and adjust statistical testing for the correlation between results of participants who contributed more than one event to the analysis. The comparison of slopes of the ammonia decline curves by treatment group will shift to secondary analysis, which will allow us to focus on consistency of results rather than choosing the precise model for significance testing for the purpose of rejecting the null hypothesis of no treatment effect.

Study analyses will be based on an intention-to-treat paradigm. In analyzing the primary outcome, we will evaluate the difference over time in the probability of reaching an ammonia level of 50 $\mu\text{mol/L}$ or hospital discharge. For this purpose, we will use a z-test to assess the evidence that the hazard (event) ratio (HR) differs from 1 (no effect) to test for a difference in the probability of the composite outcome over time by the group. We will account for the correlation between repeat episodes per participant by treating participant episodes with the same ID as a cluster, which will adjust standard error estimates for the intraclass correlation between episodes in the same cluster. The primary analysis will be implemented using the sts cox procedure in Stata 14 (StataCorp. *Stata Statistical Software: Release 14*, College Station, TX: StataCorp LP, 2015).

Secondary efficacy outcomes are based on groupwise comparisons of the trajectory (slope) of ammonia decline, FSS, and time-to-hospital-discharge during hyperammonemia episodes. For analysis of the ammonia decline trajectory and FSS analysis, we will implement longitudinal linear hierarchical models. The models will enable us to estimate and compare the slope(s) based on ammonia change trajectory over time, as well as the time, averaged FSS across all episodes treated with NCG vs. PLBO. For time to discharge comparisons, we will rely on the same Cox Regression Analysis described for the primary outcome except the outcome event will be limited to time to discharge. As in the primary analysis, we will adjust model error for the clustering of observations by patient and control for severity based on ammonia level or FSS at admission to each episode. To assess NCG safety we will compare the levels/frequency of laboratory test results, reported symptoms, and adverse events. Secondary analyses will control for indicators of episode severity, e.g. peak ammonia.

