1.2 Study Rationale

As described above, current drug therapy for inherited hyperammonemia relies mainly on the activation of alternate pathways for nitrogen elimination. In contrast, N-carbamylglutamate (NCG), a stable analog of N-acetylglutamate, catalytically stimulates the urea cycle, thus converting many more molecules of ammonia to urea with a relatively small dose of the drug. This represents a paradigm shift in the medical treatment of hyperammonemia.

A drug that could repair or stimulate a dysfunctional urea cycle would have several advantages over current therapy. First, it would intervene through the normal pathway of ureagenesis, which is catalytic rather than stoichiometric. Second, it may not need to replace current treatment but would be complementary to it. Third, the ability to stimulate residual ureagenesis could benefit many conditions that cause hyperammonemia, not just a single disorder. Enhancement of residual ureagenesis capacity in patients with hyperammonemia would markedly alter the natural disease course resulting in a manageable phenotype and better clinical outcome.

Our recent studies show that ureagenesis is augmented by NCG in healthy individuals and in more than half of all individuals with inborn errors that were tested.

The eligibility for the studies in this study specifically includes severe PA and MMA and “milder” CPSD and OTCD, which may appear paradoxical. However, the rationale for these selection criteria is based on the different mechanism(s) of action in these disorders. Significant hyperammonemia in PA or MMA is usually seen only in the most severely affected patients who present as newborns. Patients with hypomorphic alleles have milder disease and are unlikely to have serious hyperammonemia.⁷² In severely affected patients with PA and MMA, NCG works to alleviate deficiency of NAG created by the inhibition of NAGS by the mitochondrial accumulation of propionyl-CoA, hence, the more profound the NAG deficiency, the more robust the NCG effect. In CPSD and OTCD however, the putative effect of NCG relies on stimulating residual CPS1 or OTC activity. Indeed, when these enzymes are totally absent, no amount of NCG would help, hence, the need to enroll patients with partial rather than complete enzyme deficiencies.

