8.4 Rationale for Sample Size and Statistical Power

All sample size and power estimates are based on 2-tailed testing, which assumes a type 1 error of 5% and achieving 80% power to detect an HR difference by treatment group and that there is no censoring as each episode will contribute information to one of the composite outcomes. We used the Cox Regression procedure in PASS (Hintze, J. PASS 11. NCSS, LLC. Kaysville, Utah, USA. www.ncss.com, 2011) to evaluate the composite time to event outcome of the earlier of the time to reach an ammonia level of 50 μ mol/L or time to discharge within hyperammonemic episodes (the unit of randomization and analysis). We evaluated HR estimates above 1, reflecting that the NCG group achieved the higher probability of achieving the composite event. Based on these considerations, a total sample size of N=146 episodes can detect an HR of 1.6, one of N=114 can detect an HR of 1.7, one of N=93 can detect an HR of 1.8 and one of N=78 can detect an HR of 1.9. These sample size estimates account for an inflated R-square as large as 0.05 between the time to event outcome and covariates reflecting baseline severity at the start of an episode. We used the inflated R-square to account for the modest effect of clustering of episodes within a person. Therefore, we consider the originally-targeted sample size of 144 episodes to be more than sufficient to meet the aims of the study. Based on our re-analysis of the time-to-event outcome, an HR of 1.7 is realistic and a sample size of 114 episodes is sufficient to detect that effect. Therefore, the target sample size will be 114 episodes.

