10.3.4 REDCap Randomization

At each episode, online checks ensure all episode eligibility criteria are met, and if so, access is provided to the REDCap randomization button. When pressed, the button implements an online program that accesses a pre-generated, encrypted, randomization schedule created by the CNMC Division of Biostatistics and Study Methodology to make the appropriate treatment assignment for that subject. This procedure will provide a balanced allocation of assignments to each treatment arm over the episodes. Once an assignment is made, to maintain the blind the person enrolling the subject will be notified simply that the site pharmacy is preparing the assigned medication. These procedures will ensure tamper-proof, blinded randomization as well as overall balance in assignment to treatment groups. The Site Pharmacy will simultaneously receive online or fax notification of the assignment and will be requested to prepare the appropriate dosing kit for pick-up or delivery to the floor (depending on site logistics).

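### The Cox models leave out disorder group (PA/MMA versus CPSD/OTCD); if it is prognostic beyond baseline severity, one prespecified term would recover power at little cost

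*Combined protocol and SAP*

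**What the plan says.** Section 8.3 says the primary Cox model will "allow us to control for differences in severity (ammonia level and or FSS) at episode baseline", with repeat episodes handled by clustering on participant. The time-to-discharge analysis uses the same Cox model, again controlling only for severity (ammonia or FSS at admission, with peak ammonia given as an example for secondary analyses generally). Section 8.3.1 runs the interim look by the same methods. Section 8.4 mentions only covariates for severity at the start of the episode. Section 8.2 gives site as the only stratification factor. Disorder is named in none of these places.

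Disorder is established at eligibility (Section 4.1). Section 3.1 ties it to background care: "Ammonia scavengers may only be administered in patients with urea cycle disorders". Section 6.6.1 prohibits these drugs in PA and MMA, and Section 6.6.2 allows them in CPSD and OTCD.

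**The concern.** Two episodes with the same starting ammonia and FSS can receive different ammonia-lowering background care solely because of the diagnosis. Treatment given after baseline is not captured by a baseline severity score. Section 1.1.7 counts scavengers among the main current treatments. Discharge, the other half of the composite, also depends on complications, and the list in Section 7.1.1.3 (pancreatitis, cardiomyopathy, renal dysfunction and others) is specific to PA and MMA. A difference between disorder groups in time to the endpoint, whichever arm is assigned, is therefore plausible.

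In a Cox model, leaving out a prognostic factor moves the estimated treatment hazard ratio toward 1 relative to its value within levels of that factor, even when the arms are perfectly balanced. What is at stake is power. Section 8.4 lowers the target from 144 to 114 episodes, which leaves little reserve.

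**Working it through.** **Inputs from the documents (Section 8.4 unless noted).** The error rates are "2-tailed testing, which assumes a type 1 error of 5% and achieving 80% power to detect an HR difference by treatment group". The target is "one of N=114 can detect an HR of 1.7". Events equal episodes, because "there is no censoring as each episode will contribute information to one of the composite outcomes". On covariates: "These sample size estimates account for an inflated R-square as large as 0.05 between the time to event outcome and covariates". Allocation is taken as 1:1 from Section 10.3.4: "This procedure will provide a balanced allocation of assignments to each treatment arm over the episodes". The synopsis gives 36 patients, so 114/36 = 3.2 episodes each.

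**Reproducing 114.** Schoenfeld events = (1.960 + 0.842)² / [0.25 × (ln 1.7)²] = 7.849 / (0.25 × 0.2816) = 111.5, or 112.
- Divided by (1 − 0.05): 117.4, or 118.
- Divided by (1 − 0.02): 113.8, or 114. The same R-square of 0.02 also returns the stated 146, 93 and 78.
- Power at 114 with R-square 0.05: Φ(√(114 × 0.95/4) × 0.5306 − 1.960) = Φ(0.801) = 78.9%. With the final bound of 1.9686 it is 78.6%.

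The plan's figure is therefore reproduced to within about a point of power, with nothing to spare.

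**Assumptions not in the documents.** The documents give neither the effect of disorder on time to the endpoint nor the planned mix of disorders. I therefore vary the ratio of resolution rates between disorder groups (1 to 3) and the share in one group (50% or 30%).

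**Simulation of the planned model.** Exponential times, no censoring, 36 patients with 114 episodes, 57 per arm, and treatment HR 1.7 within each disorder group. The fitted model has treatment and a baseline severity covariate (true log-HR −0.3 per SD), with and without disorder, and cluster-robust errors. There were 2,000 runs per row with critical value 1.96. The Monte Carlo error is about √(0.8 × 0.2/2000) = 0.9 points per power figure.

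| Disorder ratio, given severity | Power without → with disorder, 50% share | Gain | Power without → with, 30% share | Gain |
|---|---|---|---|---|
| 1.0 | 80.8 → 81.0 | 0.2 | 79.0 → 79.1 | 0.1 |
| 1.5 | 77.8 → 80.0 | 2.2 | 76.9 → 79.6 | 2.7 |
| 2 | 74.6 → 81.0 | 6.4 | 72.4 → 77.2 | 4.8 |
| 3 | 64.8 → 80.0 | 15.2 | 69.0 → 78.7 | 9.7 |

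The large-sample HR without disorder (200,000 episodes) is 1.68–1.70 at ratio 1.5, 1.62–1.66 at ratio 2 and 1.57–1.60 at ratio 3.

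**If severity carries part of the difference.** Further runs used the final bound of 1.9686, a 50:50 mix and robust errors.
- Independent of severity: gains of about 2, 6 and 12 points at ratios 1.5, 2 and 3.
- Half carried by severity: gains of about 1, 2 and 5 points.
- With a stronger severity effect (log-HR 0.5 per SD, 3,000 runs) at raw ratio 2: 71.5% v 79.3% with none carried, 77.8% v 80.4% with half and 79.2% v 79.6% with all. At ratio 1.5 with half carried: 78.5% v 78.9%.

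**Correlated episodes.** With a patient effect of variance 0.3 on the log-hazard scale, ratio 2 and a 50% share, power is 58.4% without disorder and 65.3% with it. Both are lower for a reason separate from this point, but the gain remains.

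**Under no treatment effect.** The mean HR is about 1.00 with or without disorder. Type I error with robust errors is 5.7–7.0% without the term and 6.0–7.6% with it. The largest rise is from 6.0% to 7.6%, at a 50% share and ratio 3.

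**Cost when disorder is irrelevant.** At ratio 1 the change is +0.1 to +0.2 points with robust errors. With model-based errors it is −0.6 points (80.4 → 79.8 and 78.2 → 77.6).

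**The case against.** A reader might infer that the pooled hazard ratio is certainly attenuated and the trial underpowered. The documents do not support that. They give no evidence on whether disorder predicts the endpoint once ammonia and FSS are in the model, so a loss of zero is within range. Where severity carries the whole difference, little remains to recover. This objection stands and makes the point conditional.

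A reader might also take Section 1.2 as proof that disorder is prognostic. Its statement that "the rationale for these selection criteria is based on the different mechanism(s) of action in these disorders" is mainly about how NCG acts. It bears on whether the treatment effect differs by disorder, not on how fast episodes resolve whichever arm is assigned. The scavenger rule is firmer ground, but the documents do not say which group resolves faster.

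Third, Section 8.4 calls 1.7 realistic from a re-analysis, without saying whether it is a within-disorder or pooled value. If it is pooled, any dilution is already in it, and the term would add power above plan instead of restoring a shortfall. That changes the description, not the case for the term.

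Finally, a reader might infer confounding or an invalid test. Neither follows. Episodes are randomized, chance imbalance is part of the standard error, and the null runs show no bias. The smaller hazard ratio reflects non-collapsibility.

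The objections do not touch the asymmetry: close to nothing is lost if disorder is irrelevant, and several points are gained if it is moderately prognostic.

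**Conclusion.** The point holds as a conditional efficiency gain. Disorder group is a known pre-randomization factor, tied by protocol to background care, and is used in neither the models nor the stratification. At 114 episodes, within-disorder HR 1.7 and a 50:50 mix, omitting it costs about 2 power points at ratio 1.5, about 6 at ratio 2 (7.8 in one set-up) and 12 to 15 at ratio 3 when the difference is independent of severity. It costs roughly 1 to 5 points when severity carries half, and none when disorder is not prognostic. A 30:70 mix gives smaller losses at ratios 2 and 3.

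These sizes rest on assumed ratios and mixes, proportional hazards and a common treatment effect. The planned test is valid as it stands. The change is advisable but is not needed for validity.

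**What to change.** In Section 8.3, prespecify disorder group (PA/MMA versus CPSD/OTCD) alongside baseline severity in the primary, interim and time-to-discharge Cox models, either as a fixed covariate or as a Cox stratum. A stratum avoids assuming proportional hazards between disorder groups. Fix the choice before any comparison by arm is seen, so that it cannot look like model selection. The same edit should replace the open and/or choice between ammonia and FSS with named severity covariates.

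The cost is one sentence and one variable already collected. The statistical price is under 1 power point if disorder is not prognostic, and possibly a slightly higher type I error from robust errors with about 36 clusters. A main-effect term does not address treatment effects that differ by disorder; that question would need its own analysis.
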